The STELLA Intervention. STELLA consists of 8 sessions: 4 sessions one-to-one, with the Care Partner and a Guide, and then 4 sessions with one Guide with up to four Care Partners (total small group will include as few as two and as many as 4 Care Partners) (**Table 2**). Each weekly session takes about 1 hour. The first four sessions allow for development of the Care Partner-Guide working relationship. In these sessions, the Care Partners identify behaviors (both the person with dementia's and the Care Partner's) which are upsetting to the family. Care Partners will be taught to use an "ABC" approach to identify activators of behaviors, the behaviors, and consequences of the behaviors. After they identify the ABCs, they will develop a plan to address the behavior and then test it. Based on Care Partner feedback from our pilots, we adapted the prototype intervention so that STELLA uses the ABC plan for both the person with dementia behaviors *and* Care Partner behaviors. After the four one-to-one sessions, Care Partners will meet in small groups with a Guide. Effective communication strategies, engagement in pleasant events, and coping will be addressed (**Table 2**). ⁽⁷⁾ The Guide will facilitate conversation and support between the Care Partners. Care Partners will be provided with each other's contact information. They will be encouraged to contact each other during and after the intervention. Due to schedule conflicts, there may be an up to two-week gap between Sessions 4 and 5.

Each Care Partner will have their own STELLA workbook to document their plans and progress (see "The STELLA Collaborative Handbook"). The booklet will be given or mailed to them prior to the first STELLA visit. They will have access to information on caring for person with dementia on the STELLA password-protected website which is under production. STELLA allows for some flexibility in scheduling if Care Partners have to re-schedule. Care Partners will be advised that the one hour sessions may be tiring and that they may end a session early if needed. In addition, Care Partners will need to find an activity for their care-recipients while they are engaged in the training session so they can focus on the material and protect their care-recipients' dignity. Some of the conversations will include discussions about challenging behaviors, which if overheard by the care recipient, may be upsetting.

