ZBI ³³	
CESD-10 ³⁴	
MMCGI-SF ³⁵	
Placement plan scale ³⁷	
QoL-AD	
STELLA contact	STELLA care partner contact post intervention
STELLA Experience Survey	16-item + comments on satisfaction, privacy, ease of use
Earth Assessment	
RMBPC ²³	
 • See Baseline for descriptions • Baseline: 
 + STELLA contact survey -Experience Survey
ZBI ³³	
CESD-10 ³⁴	
MMCGI-SF ³⁵	
Placement plan scale ³⁷	

QoL-AD	-Demographic survey
STELLA contact	

Phase 2

Aim 1. Quantify the costs of delivering the STELLA intervention. This will measure the direct costs of delivering the intervention (wage multiplied by time of all personnel supporting the intervention) as well costs of technology and equipment, and any in-kind donations of equipment or time to support the intervention.

Aim 2. Quantify the cost efficacy of STELLA in relation to BPSD frequency and CP reactivity and assess the relationship between costs, BPSD, and care partner burden.

Out-of-pocket costs for participating dyads will be collected using an addition to the weekly online ORCASTRAIT survey. CPs will be queried about personal funds spent on health care services, co-pays, medications, or equipment. CP time dedicated to these care-related activities will also be collected. Implicit costs for families will be calculated by multiplying the average weekly hours of care provided by the CP by the average hourly wage of paid caregivers in Portland, Oregon (approx. \$29).

Analytic Plan.

Phase 1

Aim 1: Feasibility will be assessed by calculating the proportion of enrolled Care Partners who completed the full intervention. Reasons for drop-out and discontinuation will be investigated carefully. Focus group transcriptions will be analyzed for themes of acceptability using narrative analysis.⁽²⁵⁾

Aim 1 Anticipated Results and Implication. We anticipate that the Care Partner will find the STELLA intervention feasible and acceptable. This will provide foundational information for future proposals.

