Other quantitative analyses may be performed if they data reveal important trends.

PHASE 2

Aim 1: We will carry out a costing of the intervention to determine implementation costs of STELLA.

[figure not shown]

Figure 1: Composite model spider plot of digital behavioral biomarkers in a dyad showing potential domains associated with the degree of caregiver burden (49). Numbers are odds of having the behavior relative to low burden. Similar comparisons can be made relative to baseline (e.g. sleep time or time alone before relative to after intervention).

Aim 1 Anticipated Results and Implications. The costing will demonstrate the actual costs of delivering the intervention. This is essential for future pragmatic trials and ultimately for widespread adoption in the US health system.

Aim 2: Assess data collected from CPs for correlations between BPSD frequency and explicit costs to measure the direct cost impact of the intervention. We then assess the relationship between BPSD frequency, CP reactivity, and out-of-pocket costs for families using linear regression models and controlling for salient covariates based on preliminary correlational analysis. We will repeat this analysis for implicit costs. We will then compare both the explicit and implicit out-of-pocket costs for participating CPs to those who do not participate.

Aim 2 Anticipated Results and Implications. We expect to see a relationship between BPSD and cost. Specifically, more BPSD behaviors and more CP reactivity to the BPSD will be associated with higher out-of-pocket and implicit costs for families living with dementia. Further, we expect to find a relationship between out-of-pocket and implicit costs and objective measures of burden identified in the ORCASTRAIT Living Lab continuous home assessment. Higher objective burden will correlate with higher implicit and out-of-pocket costs. This will provide much needed data on the intervention's cost-efficacy compared to other interventions to support people living with dementia.

6. Data and Specimens.

No genetic material or specimens will be collected in this study.

a. Sharing of Results with Subjects

Results of the RMBPC and the Pre-Treatment Survey will be shared with the Care Partner prior to the intervention. This will help the Care Partner identify behaviors they want to target in the training sessions. If the memory, depression, burden or grief scores are abnormal, the Care Partner may be

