This study will be using interactive, real-time delivery of telehealth care over distance using video-conferencing equipment. The basic mode of connectivity between the study subjects and the research team will be via OHSU's WebEx system. This platform is secure as independently validated by OHSU's IT and legal department.

The Webex recording system will be used to record the telehealth visits. This service can securely record all visits as needed. There is no limit as to how many visits can be recorded concurrently. Visit recordings will be managed through the Webex secure web portal requiring OHSU credentials and multi-factor authentication. OHSU Security Engineering department has agreed to ensure that this study's policies and procedures meet strict Information Security Directives (ISDs).

Video-recordings may be shared with other researchers and those outside of OHSU who are involved in conducting or overseeing research via the secure Webex portal, or via OHSU Box.com or OneDrive. Using Webex, video streaming links can be sent to identified users via email (which will require a password to access). Study coordinators can download the video files outright from the Webex portal and saved on OHSU's "X" drive in a highly secure, biometrically authenticated data center or shared via OHSU Box.com or OneDrive. Using OHSU Box.com or OneDrive the research team will use the "Invite Collaborators." To ensure the videos cannot be downloaded, the "Invitee Permissions" will be set at "Previewer."

Electronic survey data will be stored in a web-accessible server at Qualtrics or REDCap, though copies of this data will be transferred to a secure OHSU server via API call. Other electronic data will be stored on a secure, password protected OHSU server. Access to data is restricted to study personnel. Access to data requires username/password authentication.

8. Risks and Benefits

a. Risks to Subjects

There are few risks involved in this study. Care Partners will have to meet (via telehealth) with the research team for multiple visits, which may be inconvenient. Care Partners will need to find an activity for their care recipients during the sessions, which may cause financial hardship for some. All visits will be via telehealth, so there should be no travel costs involved.

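### The Phase 2 family-cost items name neither session cover nor Care Partner session time, so the participant versus non-participant cost comparison can favour STELLA

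*Combined protocol and SAP*

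**What the plan says.** **Delivery cost.** Section 5 (Procedures Involved), Phase 2, Aim 1 counts "wage multiplied by time of all personnel supporting the intervention", together with "costs of technology and equipment, and any in-kind donations of equipment or time to support the intervention". The Analytic Plan for Phase 2, Aim 1 gives the scope: "We will carry out a costing of the intervention to determine implementation costs of STELLA". It adds: "The costing will demonstrate the actual costs of delivering the intervention". No costing perspective (provider, payer, family or societal) is named.

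**What STELLA asks of families.** Section 5, The STELLA Intervention, sets eight sessions: four one-to-one, then four in groups of two to four Care Partners. "Each weekly session takes about 1 hour". The same section states: "Care Partners will need to find an activity for their care-recipients while they are engaged in the training session". Table 1 excludes Care Partners who cannot do this. Section 8a (Risks to Subjects) says: "Care Partners will need to find an activity for their care recipients during the sessions, which may cause financial hardship for some".

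**Family cost.** Section 5, Phase 2, Aim 2 extends the weekly ORCASTRAIT survey: "CPs will be queried about personal funds spent on health care services, co-pays, medications, or equipment". Care Partner time on those activities is also collected. Implicit cost is average weekly care hours multiplied by a local paid-caregiver wage of about $29 per hour. The Analytic Plan for Phase 2, Aim 2 relates these costs to BPSD frequency and Care Partner reactivity by correlation and regression. It then compares explicit and implicit costs of participating Care Partners with those of non-participants. The result is presented as evidence on cost-efficacy relative to other interventions.

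**The concern.** The protocol recognises that attending STELLA uses family resources: the Care Partner's hour, and whatever occupies the care recipient meanwhile. Neither appears by name among the listed Aim 1 or Aim 2 cost items.

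This matters most in the comparison of participants with non-participants. Only participants incur session-related costs, so leaving them out can shift the comparison only towards STELLA.

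The implicit-cost rule can also move the wrong way. If someone else looks after the care recipient during a session and the Care Partner reports an hour less care that week, the rule records a fall of about $29, while the cover and the session hour go uncounted.

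**Working it through.** The plan states no cost total, so there is no figure to reproduce. What follows is a scale check.

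**Inputs from the documents:** 8 sessions of about 1 hour (The STELLA Intervention); groups of 2 to 4 in sessions 5 to 8 (same section); about $29 per hour (Phase 2, Aim 2); up to 40 dyads (section 4a).

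**Assumptions:** one hour of cover per session where cover is needed, priced at $29. The share of families needing cover, p, is not in the documents and is varied from 0 to 1.

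1. Care Partner session time: 8 × 1 × $29 = $232 per family.
2. Cover: 8 × 1 × $29 × p. For p = 0, 0.25, 0.50, 0.75 and 1, this averages $0, $58, $116, $174 and $232 per family.
3. Both at most: $232 + $232 = $464 per family. For 40 dyads: 40 × $464 = $18,560.
4. Guide contact hours per Care Partner: 4 + 4/g for group size g. This gives 6.0 (g = 2), 5.3 (g = 3) and 5.0 (g = 4). Eight Care Partner hours are therefore 8/6.0 = 1.3 to 8/5.0 = 1.6 times Guide contact hours. Preparation, training and fidelity review are excluded from this ratio and would lower it. No Guide wage is given, so no dollar ratio follows.

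**What the listed items would record, per session.** The session hour is valued once: if it was already reported as care, it is not added again.

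| Situation | Change recorded | Change with session time and cover | Omitted | Omitted over 8 sessions |
|---|---|---|---|---|
| Free activity, hour still reported as care | $0 | $0 | $0 | $0 |
| Free activity, reported care falls 1 h | −$29 | −29 + 29 = $0 | $29 | $232 |
| Cover used, hour still reported as care | $0 | +$29 | $29 | $232 |
| Cover used, reported care falls 1 h | −$29 | −29 + 29 + 29 = +$29 | $58 | $464 |
| Session outside usual care hours, no cover | $0 | +$29 | $29 | $232 |

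In no row does the omission count against STELLA. In the second and fourth rows a saving is recorded where there is none, or where there is an added cost.

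**Relative size.** Take a Care Partner giving 4 hours of care a week, the Table 1 minimum for those not living with the care recipient. Over 18 months (78 weeks) implicit cost is 4 × $29 × 78 = $9,048, of which $232 is 2.6% and $464 is 5.1%. Over the 8 session weeks alone it is 4 × $29 × 8 = $928, of which $232 is 25% and $464 is 50%. More weekly care hours would lower all four shares. The plan does not state the time window for the comparison.

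**The case against.** Much of the opposing case stands.

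- **Aim 1 is not understated on its own terms.** A reader might infer that STELLA's cost as defined is too low. The documents do not support that. Aim 1 is scoped as a delivery or implementation cost, and Background (Phase 2) ties it to coverage decisions by payers. Leaving out recipients' time is proper for that quantity. Aim 1 also goes beyond wages and equipment: donated time is included and could be read to cover unpaid family time, although nothing says so and no listed item would capture it.
- **No savings calculation is specified.** A reader might infer that the plan credits family time as a benefit when it falls. The $29 rate only describes weekly implicit cost. H1 and H2 are associations, and the Aim 1 figure enters neither. The asymmetry arises only through the comparison of participants with non-participants.
- **Paid cover is not required.** The text asks for an activity, which may cost nothing, and hardship is only possible. Some Care Partners live apart from the care recipient and may need no arrangement. For a family that pays nothing and still reports the hour as care, the omission is zero.
- **Pricing the Care Partner's own learning time at a replacement wage is a choice.** Results should therefore be shown with and without it.
- **The parent survey is not available here.** Table 3 refers to the ORCASTRAIT protocol for the weekly cost items, and that survey may already ask about respite or sitter costs.

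What remains is that no item listed in these documents names session cover or session time, and the planned comparison is exposed to that omission in one direction.

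**Conclusion.** The point holds for the family perspective. The Aim 1 costing is sound once labelled as a provider-perspective figure. The Aim 2 items, as listed, leave out a cost that only participants bear, so the planned family-cost comparison, and any cost-efficacy statement resting on it, can favour STELLA.

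The illustrative size is $232 per family for Care Partner session time and $0 to $232 for cover, so at most $464. It falls to zero where the activity is free and the hour is already reported as care. These figures rest on one-hour sessions, one hour of cover where needed, the plan's $29 rate, and an unknown share of families needing cover. Actual payments could differ from $29 per hour. The conclusion also assumes that the parent survey has no such item.

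The gap does not invalidate an exploratory study of up to 40 dyads. It should be closed while sessions run, because cover hours and payments are hard to reconstruct afterwards.

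**What to change.** 1. Label the Aim 1 result as the provider perspective, and state whether in-kind time includes family time.
2. Check the ORCASTRAIT weekly survey. Unless it already asks, add two items while sessions run: hours of cover arranged for the session, and amount paid.
3. Take Care Partner session time from attendance records. Do not count it again where the hour was already reported as care.
4. Report STELLA cost per Care Partner separately from the provider and the family perspective, with and without valuing time at $29 per hour.
5. Include session cover in the participant versus non-participant comparison. Keep it out of the BPSD–cost regressions, where it would reflect attendance at STELLA rather than the cost of symptoms.

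The cost is two short items for about 8 to 10 weeks (eight weekly sessions plus the permitted gap of up to two weeks after session 4), one additional set of results, and a somewhat higher family-perspective cost for STELLA.

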Dementia is the most expensive condition in the United States (US).⁽¹⁾ The high costs are driven in part by the prolonged course and intensity of the disease and heavy care demands on family members.⁽²⁾ A significant contributor to care demands are the behavioral and psychological symptoms of dementia (BPSD) (e.g., depression, irritability, agitation, anxiety) that the majority of persons with dementia (PwD) experience.⁽³⁾ These BPSD have been linked to care partner (CP) depression, burden, and grief,^(4, 5) and in turn, BPSD frequency increases when CPs are depressed and burdened.^(5, 6) De Vugt et al.⁽⁷⁾ found that CP reactivity to BPSD predicted skilled care placement, which is concerning

because skilled care makes up the largest portion of the average annual cost per person of US \$50,201.⁽⁸⁾ Despite evidence that BPSD contribute to care costs, the literature on the cost efficacy of Telehealth-based interventions for BPSD is limited. Further, while numerous technology-based interventions exist, little attention is given to implementation costs or to the potential cost savings of these interventions.

STELLA (Support via TEchnology: Living and Learning with Advancing ADRD) is an intervention designed to address the need for a personalized approach to teach CPs strategies in managing BPSD. This real-time educational intervention is designed for families caring for those in moderate to late-stages of dementia. STELLA uses videoconferencing to connect CPs, in their own homes, with experienced Guides. The Guides use cognitive behavioral techniques to assist CPs in identifying and implementing strategies to reduce distressing behavioral symptoms in the PwD. This in turn diminishes CP burden and depression.⁽⁹⁾ Our pilot work found that early versions of -STELLA reduced the frequency BPSD and CP reactivity to them.^(10, 11) The subjective and objective outcomes of STELLA are now being tested in the ORCASTRAIT Living Lab, with the goal of scaling STELLA up to address the needs of the 16 million CPs in the US. To prepare for effective future scaling of STELLA, the longer-term costs of implementing the intervention, as well as the cost benefits of the intervention need to be determined.

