Care Partner	
 Adult caring for family member with ADRD Lives with care recipient OR spends at least 4 hours/week with care recipient⁽²¹⁾ Age of 18 years or older Speak English Own a computer/device with a reliable internet connection and compatible operating system 	
 Unable to find activity for care recipient during training which would allow Care Partner to work privately, one-on-one during training Completed similar telehealth intervention within the last year Hearing and vision problems severe enough to prevent participation Unwilling or unable to adequately follow study instructions and participate in study procedures
Both	Participate in ORCASTRAIT (IRB#20236)	

c. Vulnerable populations. The primary focus of this study is to assess the feasibility, costs, and efficacy of subjective and objective measurements of Care Partner and person with dementia responses to the STELLA intervention. Therefore, in order for this study to be successful, participants with moderate to late stage ADRD will be recruited. Few interventions address the needs of families in these later stages.

We will ask that a legally authorized representative (LAR) and, if appropriate, the person with ADRD, if the person with ADRD is competent to make a decision about participation. If the LAR and/or the person with ADRD are concerned about competency, the LAR will be asked to make the participation decision. No other vulnerable populations such as children, prisoners, or pregnant women will be included in this study. All Care Partners will be 18 or older.

d. Setting. This study will take place at OHSU. Participants will connect (from their homes or another convenient location) to the research team via direct-to-home, telehealth, video-conferencing and over the telephone at the Layton Aging and Alzheimer's Disease Center. Interventionists will meet with

caregivers via videoconferencing on an OHSU computer and HIPAA secure link. The interventionist may complete the visit from his or her home, OHSU office or other convenient private location. They will use a privacy screen so that participants will not see their home or office environments. No others (e.g., family members of interventionists) will be allowed in the room during the intervention. Please see ORCASTRAIT (IRB#20236) protocol for details of living lab.

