Intervention (4 weekly sessions)	Meet with for 4 weekly sessions, beginning with Session 1 . (see Table 2)	After Mercury Baseline survey completed
Starlet Survey (Survey 2)	Electronic assessment of depression, burden	1 month after Session 1
Intervention (4 weekly sessions)	Meet with Guide and up to 4 other Care Partners for 4 more weekly sessions (See Table 2)	After session #8
Venus Survey (Survey 3)	Full assessment, including program survey	2 months after Session 1
Post-STELLA Assessment	Complete personalized target problem assessment via Qualtrics or via video or phone call with a Research Assistant	After Venus survey completed
Focus Groups	Optional focus group to provide study team with feedback	After Venus survey completed
Earth Survey (Survey 4)	Full assessment (Table 4)	6 months post-intervention
Earth Survey (Survey 5)	Full assessment (Table 4)	12 months post intervention
ORCASTAIT Surveys	Cost, burden as described in ORCASTRAIT Protocol	Weekly, while in ORCASTRAIT

Phase 1

Measures. Aim 1: Feasibility will be assessed by measuring how many Care Partners who start the program successfully complete it. Care Partners will fill out our telehealth survey that asks them about acceptability.^(23, 24) Acceptability will also be assessed qualitatively using focus groups.⁽²⁵⁾ The focus groups will be conducted via videoconferencing and will be recorded and transcribed for analysis.^(15, 16)

Aim 2: Standard quantitative measures that were used in the earlier pilots^(15, 16) will be used to provide preliminary evidence for efficacy. The quantitative measures are grouped into 5 surveys: Mercury Baseline, Starlet, Venus, Earth (6 months post intervention) and Earth (12 months post intervention). Along with the ORCASTRAIT Living Lab suite of measures (demographics, activity, time with person with dementia, sleep-related behaviors), we assess burden using the RMBPC⁽²⁶⁾ and the 22-item Zarit Burden Interview (ZBI). To provide focus for the intervention, each Care Partner will identify and rate 2-3 specific target problems to address in STELLA. Pre-death grief will be assessed with the Marwit Meuser Caregiver Grief Index, Short Form (MMCGI-SF).⁽²⁷⁾ Care Partner plans for person with dementia placement will be assessed with the

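### The Phase 2 Aim 2 cost measure can record a shift from family care to paid care as a saving, because paid-care fees are not named among the out-of-pocket items and no total cost or placement date is specified

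*Combined protocol and SAP*

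**What the plan says.** Section 5 (Procedures Involved), Measures, Phase 2, Aim 2, defines two family costs.

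- **Out-of-pocket:** "Out-of-pocket costs for participating dyads will be collected using an addition to the weekly online ORCASTRAIT survey". On content, "CPs will be queried about personal funds spent on health care services, co-pays, medications, or equipment". Residential care, paid in-home care and respite are not named, and the scope of health care services is not defined.
- **Implicit:** obtained by "multiplying the average weekly hours of care provided by the CP by the average hourly wage of paid caregivers in Portland, Oregon", put at about $29.

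The Analytic Plan (Phase 2, Aim 2) regresses out-of-pocket cost on BPSD frequency and reactivity, repeats this for implicit cost, then compares both costs between participating and non-participating Care Partners. It defines no sum of the two.

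On placement, Table 4 has one item on plans. No placement event, date or rule for later weeks is described. The Background (Phase 2) reports that Care Partner reactivity predicted skilled-care placement and that "skilled care makes up the largest portion of the average annual cost per person", a figure of $50,201. The anticipated results for Phase 1 Aim 2 include a reduced desire to place.

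**The concern.** Care can pass from the Care Partner to someone who is paid. The implicit-cost formula registers the hours given up but not what replaces them. If the replacement is paid for by the family and the survey does not pick it up, the recorded cost of that dyad falls although the family may be spending as much or more.

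This matters because such shifts may not be random with respect to the questions asked. H1 relates BPSD and reactivity to both cost types, and the protocol's own background ties reactivity to placement. STELLA is expected to lower the desire to place, so the participant versus non-participant comparison may be touched as well. Participants have moderate to late dementia and are followed for 18 months, so changes in care arrangements are plausible. The Background also presents the cost results as a step towards coverage by payors.

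**Working it through.** The protocol states no total cost, power or effect size for this aim, so there is no figure to reproduce.

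**Inputs from the protocol:** $29 per Care Partner hour (Measures, Phase 2, Aim 2); $50,201 average annual cost per person (Background, Phase 2). **Assumed:** weekly hours before and after the shift, and the share of any fee that the family pays.

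**1. Fall in implicit cost** = (hours before − hours after) × 29.
- 40 to 5 hours: 40 × 29 = 1,160; 5 × 29 = 145; fall of $1,015 a week.
- 20 to 5 hours: 20 × 29 = 580; 580 − 145 = $435 a week.

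These are drops in valued family time and would be the same if every fee were recorded. They are not the bias. The bias in family cost is the family-paid fee that is not recorded.

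**2. A case without placement.** Suppose a family hires an aide for one hour, one for one, at $29. Implicit cost changes by −29 and spending by +29, a true net change of 0. If the payment is not captured, the record shows −29. This dyad stays at home and in the parent study. Section 8a also accepts that occupying the care recipient during sessions may be a financial strain for some, yet no respite or sitter item is listed.

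**3. What counting a fee would do.** No facility fee or family share is given. As a scale only, let the family pay a fraction of $50,201 a year. Fee per week = share × 50,201 / 52. Break-even fall in hours = weekly fee / 29. Net change = fee − fall in implicit cost (negative is a saving).

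| Assumed family-paid share | Fee per week | Break-even fall in hours per week | Net per week, 40 to 5 h | Net per week, 20 to 5 h |
|---|---|---|---|---|
| Fee not recorded | $0 | n/a | −$1,015 | −$435 |
| 25% | $241 | 8.3 | −$774 | −$194 |
| 50% | $483 | 16.6 | −$532 | +$48 |
| 75% | $724 | 25.0 | −$291 | +$289 |
| 100% | $965 | 33.3 | −$50 | +$530 |

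So an unrecorded fee always makes a shift to paid care look cheaper than it is. Whether it also turns a net cost into an apparent saving depends on hours and payer share, neither of which the documents supply.

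**4. Separate analyses.** Even with all fees captured under out-of-pocket cost, the implicit-cost regression on its own would show only the fall. With no sum reported, the offset would have to be pieced together from two models.

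**The case against.** The strongest reply is that omission is unproven. The protocol summarises the survey addition and does not reproduce it. Health care services could be taken to include skilled care, and Table 3 lists weekly parent-study surveys covering "Cost, burden as described in ORCASTRAIT Protocol", whose items are not in the documents. This stands: what is shown is that the plan does not ensure capture, not that fees are missed.

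Second, a fall in Care Partner hours is a correct measurement of family time, and the plan never adds the two costs. That also stands, and is why the dollar figures in step 1 are not presented as bias.

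Third, post-placement data may not exist. Weekly surveys run only while the dyad is in ORCASTRAIT, which uses home sensors, so placed dyads may be missing instead of cheap. Eligibility does not require co-residence ("Lives with care recipient OR spends at least 4 hours/week with care recipient"), so continued data are possible; the protocol does not say which applies. Missingness tied to placement would need a rule too, and the paid-aide case is unaffected.

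Fourth, the only form described as recording weekly caregiving hours is the baseline demographics form, dropped from the Venus and Earth surveys. If implicit cost used baseline hours alone, it would not move at placement. The Measures text also collects time on care-related activities alongside the spending questions, so the source of the hours is unclear.

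A reader might infer that the rule does score placement as a saving, that H1 is biased towards zero or reversed, or that the cost-efficacy answer has the wrong sign. The documents do not support this. The Background links reactivity to placement but gives no placement rates, the anticipated effect is on desire to place and not on placement itself, and step 3 shows that placement can remain a net family saving with fees counted.

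**Conclusion.** The point holds as a gap in measurement. Taken as written, care moved from the Care Partner to paid help lowers implicit cost by about $29 an hour, the matching payment is not a named item, and neither a total nor a placement date is there to reveal it. It may distort the H1 regressions and the participant versus non-participant comparison. Direction and size cannot be computed from the documents. The $1,015 and $435 a week rest on assumed hours and describe valued time; the $50,201 is an average cost per person, not a facility fee or a family share. This conclusion assumes that implicit cost uses hours updated during follow-up and that at least some paid-care spending falls outside the survey items. For an exploratory study of up to 40 dyads with no powered cost endpoint, this is a cheap improvement, worth making early because unrecorded spending is hard to recover later.

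**What to change.** - Name residential or skilled care, paid in-home care and respite as three separate items in the weekly cost addition. If the parent survey already asks for them, cite those items.
- Record the date of any placement.
- Report out-of-pocket plus implicit cost alongside the two separate analyses. It need not replace them, since H1 and H2 name the two costs individually.
- State how weeks after placement enter the cost analyses. Add a pre-placement-only analysis as a sensitivity check, labelled as conditioning on a post-baseline event that the intervention may affect and so open to selection bias of its own.

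The cost is three survey items, one date field, one extra summary and one sensitivity analysis. The downside is a slightly longer weekly survey.
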